11.0 Early Withdrawals and Dropouts

Intention-to-treat analysis, which focuses on all randomized patients with at least one follow-up evaluation, will be used as this has been the standard approach used by many researchers and regulatory agencies. For either, or both HS and LS treatment phases of this crossover trial, when a patient drops out without having any follow-up data assessed, data points for the patient will be excluded from the analysis. Due to the nature of the pilot study with a relatively small population, we expect that virtually all patients enrolled in the study will return for a follow-up visit, thus the number of dropouts is likely to be far less than ~20% which we built into our samples size by consenting 22 patients with goal of having at least 18 subjects' data for both treatment phases. Dropouts will be defined as patients who are randomized but never return (i.e., there is no follow-up visits).

Possible confounding could occur when a patient is included in the analysis of phase 1 and excluded from phase II due to dropout. We will re-assess baseline balance between patients who are excluded in phase I and in phase II on demographic or clinical characteristics of patients to examine potential confounding by dropouts. For patients who are withdrawn or lost to follow-up after being randomized, the last visit after baseline screen will be used to replace missing values (last observation carried forward, LOCF method). ANCOVA with LOCF method will be used to analyze the data as a more conservative approach. Exploratory analyses will also be performed by examining the findings in the subset of subjects who are adherent to the diet (\pm 20% of target Na intake).

If the participant at any time requests to withdraw from the study, he or she may do so. We will continue to store and use samples and information obtained before withdrawal unless the participant notifies the principal investigator in writing with a date of notice. In the event of withdrawal from the study, no additional collection of information from the date of withdrawal will be performed. We will enquire from participants who withdraw whether they may be contacted for future studies.

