4.0 General Approach

Our approach will be to gather data on vascular (including blood pressure, augmentation index, vascular stiffness, endothelial function), inflammation (including DAS28, IL-17, IL-6, TNF- α), metabolic (including insulin, glucose, catecholamines), microbiome (stool and saliva), oxidative stress (F2 isoprostanes excretion), and tissue Na^+ measures after, a high-salt and low-salt intake each administered for 8 weeks, in random order, in a crossover study with a 4-week washout period between high-salt and low-salt diets in 22 patients with moderately active RA. It is not possible to blind patients to diet - thus patients and the dietitian will know whether a diet is high-salt (HS) or low-salt (LS). However, we will ensure that investigators performing assessments are blind to the dietary intervention.

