5.0 Methods

Subjects and recruitment: Patients with RA will be recruited from the rheumatology clinics of the Vanderbilt University Medical Center, by word of mouth from the practices of physicians of the Vanderbilt Rheumatology Practice, from the private practices of community rheumatologists, and by advertising. MyHealth@Vanderbilt and other VUMC-based advertising methods may be utilized. Inclusion criteria will be used to search eStar for

potential participants. Once identified, we will contact the patient's physician to ask for an introduction, with the patient's permission.

a. Inclusion criteria

1. Male and female patients older than 18 years who are willing to participate.
2. Satisfy the ACR criteria for the diagnosis of RA.
3. Have stable disease activity as evidenced by no clinically meaningful change in immunomodulating or corticosteroid therapy in the past 1 month.
4. Have moderate disease activity as reflected by a minimum of 3 swollen and tender joints.

b. Exclusion criteria

1. Pregnancy
2. Receiving dialysis
3. Organ or bone marrow transplant
4. Taking diuretics, uncontrolled hypertension ($>160/100$ mmHg), or cardiac failure requiring treatment.
5. Severe edema (as judged by the investigator)
6. Diabetes mellitus treated with an insulin pump
7. Major surgery within the previous 3 months
8. Severe co-morbid conditions such as active cancer likely to compromise study participation
9. Unwillingness, or other inability, to cooperate
10. Contraindication to MRI
11. Presence of a condition that could make 24-hour blood pressure monitoring difficult: atrial fibrillation, inability to operate machine, receiving anticoagulants, presence of a condition that in the opinion of the investigator may be exacerbated by blood pressure cuff inflation (e.g., lymphedema).

c. Screening, randomization, and blinding

Patients will be screened for eligibility and those who wish to participate and provide informed consent will enter the study.

d. Design

This will be a random-order, 2-period crossover study with washout.

e. Concomitant therapy

Patients will continue to receive their regular therapy for RA. If a patient's disease flares and requires a significant change in therapy, the subject will be withdrawn from the study, and we will have the patient return for an exit visit.

[figure not shown]
f. Dietary regimen

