The order of high-sodium (HS) or low-sodium (LS) diets will be randomized. Patients will be randomly assigned to be on the high-sodium diet (200mmol/24hours x 8weeks) or low-sodium diet (50mmol/24hours x 8 weeks) with crossover separated by 4-week washout period. We will allow a 7-day window on the diet (i.e., to facilitate scheduling the diet can be between 7-9 weeks), and we will allow a 1-week window for the washout

(i.e., washout can be 3-5 weeks). Subjects will choose a rotation of low-sodium meals from a predetermined list from a commercial vendor (Mom's Meals) that will be used to provide 2 meals (lunch and dinner)/day that the vendor will deliver at approximately 7 day intervals. If there is disruption in shipping the meals, the dieticians will direct the participants on which foods to purchase to continue the diet without interruption. Participants will be reimbursed for needed diet purchases upon submission of receipts.

Staff of the Vanderbilt Diet, Body Composition, and Human Metabolism Core (under the supervision of [name]) determine breakfast and snacks appropriate for the HS and LS diets and provide instructions to subjects. These Na^+ intake levels are in the range of high current intake estimates (~12 g/d) and AHA recommendations (~4 g/day). HS and LS phase menus will be standardized for potassium and calorie composition and will be similar in the HS and LS phases except for the addition of table salt and salty snacks during the HS phase. Treatment order will be randomized with each diet treatment for a period of 8 weeks and a 4-week wash-out period between treatments. To facilitate diet conformity we will provide patients with salt packets and high-salt snacks or drinks, and we will also purchase and provide a supply of a low-sodium breakfast for patients (e.g., a selected breakfast cereal). These items will be curbside pickup for participants on Visit 1 and 3 from the Metabolism Core. Study personnel will communicate with patients at approximately 1-2 week intervals during the HS and LS diets to provide nutrition counseling, resolve problems, optimize diet adherence, and coordinate visits. If patients feel hungry or lose weight on the prepared meals, study dietitians will provide patients with a list of allowable supplementary dietary items that patients can prepare at home and add to the prepared meals and snacks provided. During the washout period (weeks 9-12) subjects will resume their habitual diet.

Schematic of Crossover Design

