12.0 Statistical Analysis

Baseline characteristics will be summarized for patients who are randomized to the two treatments (HS vs. LS) at baseline. A crossover design eliminates confounding due to uneven distribution of baseline variables because a patient serves as his/her own control, thus a complete balance in baseline data is obtained in the absence of dropouts.

The outcomes of interest are the comparison of the change in blood pressure, vascular stiffness (Aix, PWV), endothelial function (PAT), insulin resistance (HOMA), skin Na^+ concentrations, and inflammation (DAS28 score) between baseline and 1) after 8 weeks of HS diet, 2) after 8 weeks of LS diet. We will use Analysis of Covariance (ANCOVA) which is a form of multiple linear regression model including the blood pressure at the end of each treatment (HS and LS) or the last observation for patients with early withdrawal as an outcome variable, group variable (HS or LS) as a main independent variable, and baseline blood pressure as a covariate. By including the baseline value as a covariate, the regression coefficient for the group (HS or LS) becomes the between-group (HS vs LS) difference in the change in blood pressure response. This method is often superior to the method that used the change in blood pressure directly as the outcome variable (such as student's t-test for the change) because it adjusts for baseline differences as a covariate which reduces measurement errors more effectively.

A similar approach will be used for the vascular stiffness (Aix, PWV), endothelial function (PAT), insulin resistance (HOMA), and inflammation (DAS28 score) and skin Na^+ concentrations.

If unequal distribution of some of the variables is detected by the univariate analyses of baseline characteristics between groups, those variable will be included in a multiple linear-regression model in addition to a set of a prior chosen covariates based on clinical relevance such as age, sex, and race, with knowledge of not overfitting the model

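### The only planned check for confounding by dropout compares two groups of excluded patients, so it cannot show whether lost patients differ from retained ones or whether loss depends on diet

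*Combined protocol and SAP*

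**What the plan says.** Section 11.0 (Early Withdrawals and Dropouts) states the risk: "Possible confounding could occur when a patient is included in the analysis of phase 1 and excluded from phase II due to dropout". The next sentence gives the check: "We will re-assess baseline balance between patients who are excluded in phase I and in phase II", in terms of demographic and clinical characteristics, and its stated aim is "to examine potential confounding by dropouts".

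Other parts of the document bear on who is lost and how they are counted:

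- Section 5.0, f (Dietary regimen): "The order of high-sodium (HS) or low-sodium (LS) diets will be randomized". Each phase therefore contains patients on both diets.
- Section 4.0 (General Approach): "It is not possible to blind patients to diet".
- Section 5.0, e (Concomitant therapy): if a flare needs a significant change in therapy, "the subject will be withdrawn from the study, and we will have the patient return for an exit visit".
- Section 11.0 leaves out a patient's data for a phase that has no follow-up. It carries the last observation forward for patients withdrawn or lost, and it defines dropouts as randomized patients who never come back.
- Section 12.0 (Statistical Analysis) says that with a crossover "a complete balance in baseline data is obtained in the absence of dropouts". It summarizes baseline by randomized diet and allows variables that are unequal between groups into the model.
- On numbers, Section 11.0 has 22 patients consented to yield 18 with both phases. Section 10.0 plans to enrol 50 in the expectation of many dropouts, assumes under 20% loss, and replaces losses beyond the estimate.

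**The concern.** The risk is named correctly, but the check does not address it. To learn whether loss has distorted the HS-LS comparison, one must know whether the patients lost differ from those kept, and whether loss was more common on one diet. The written check sets one group of lost patients against another, with no retained group. It groups them by phase, and phase is not diet.

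This matters because loss here may be related to outcome. A flare that needs a significant change in therapy leads to withdrawal. DAS28 is one of the two outcomes that set the sample size, and Section 3.0 hypothesizes that sodium affects inflammation. Patients also know which diet they are on. Section 12.0 itself makes freedom from dropout the condition for balance. If the check reports no imbalance, a reader will take that as reassurance on a question it did not ask.

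**Working it through.** **1. The plan's own figures.** The plan attaches no number to this check. The nearest figure is the dropout allowance in Section 11.0: 22 − 18 = 4 losses, and 4/22 = 18.2%, which agrees with the stated limit of under 20%. Section 10.0 gives a second basis of 50 enrolled. A 20% loss there is 10 patients. If only 18 complete, the loss is 50 − 18 = 32.

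**2. What the written contrast estimates.** Let μ be the mean of a baseline variable in retained patients, μ + δ₁ the mean in those excluded in phase I, and μ + δ₂ the mean in those excluded in phase II. The written check estimates (μ + δ₁) − (μ + δ₂) = δ₁ − δ₂. The retained mean cancels. If δ₁ = δ₂ = δ, the expected contrast is zero for any δ. Diet does not appear in the expression.

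**3. Size.** These assumptions are not in the documents:

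- Lost patients differ from retained ones by 1 SD on a baseline variable, equally in both phases.
- Losses split evenly between phases.
- A two-sample t-test is used, two-sided at 5%.

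Power comes from the noncentral t distribution with df = n₁ + n₂ − 2 and noncentrality d·√(n₁n₂/(n₁ + n₂)). For the written check d = 0. For lost versus retained d = 1:

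- 4 v 18: √(72/22) = 1.81, df 20
- 10 v 40: √(400/50) = 2.83, df 48
- 32 v 18: √(576/50) = 3.39, df 48

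| Enrolled | Lost in phase I v phase II | Written check flags | Lost v retained | Power |
|---|---|---|---|---|
| 22 | 2 v 2 | 5% | 4 v 18 | 41% |
| 50 | 5 v 5 | 5% | 10 v 40 | 79% |
| 50 | 16 v 16 | 5% | 32 v 18 | 91% |

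Simulation with 20,000 replicates agreed: 5.1% in each row for the written check, and 40.6%, 79.4% and 91.4% for lost versus retained. The written check stays at its false-positive rate however many are lost.

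**4. Loss by diet.** Assume an equal split between diets in the first phase and all losses on one diet. With 4/11 v 0/11, Fisher's exact two-sided p = 2 × C(11,4)/C(22,4) = 660/7315 = 0.09. With 10/25 v 0/25, p = 0.0006. The written check uses no diet information and cannot register either pattern.

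**5. Is it covered elsewhere?** Section 12.0 summarizes baseline by randomized diet and may adjust for measured imbalance. That could lessen the effect of some measured differences, but it does not compare lost with retained patients. No section does so, and none tabulates loss by diet.

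**The case against.** Five points can be made for the plan.

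- **The sentence may be a slip.** The sentence before it contrasts inclusion in one phase with exclusion from the other, so the authors may have meant excluded versus included. This is plausible, but the document does not say so. That reading would mend only half the problem, because diet would still be absent.
- **Small numbers.** A reader might infer that the written check could never reach 5% significance because at most 4 patients will be lost. The documents do not support this. The 18 completers are a goal rather than a floor, Section 10.0 plans 50 enrolled with many dropouts, and no test is named. An exact test at 2 v 2 cannot go below 2/6 = 0.33, but at 4 v 4 it can reach 2/70 = 0.029. The fault lies in which groups are compared.
- **The replacement is also weak with few losses.** This stands. At 4 losses it has 41% power for 1 SD, and even 4 v 0 by diet gives p = 0.09.
- **Flare withdrawals may not be excluded.** This stands in part. The exit visit and the last-observation rule may keep such a patient in that phase's analysis. However, the document does not list what the exit visit measures, and a flare in phase I still leaves phase II unobserved.
- **Blood pressure.** A reader might infer that patients are also withdrawn for high blood pressure on one diet. The document states no such withdrawal rule. Section 7.0 asks patients to call if a home reading exceeds 160/100 mm Hg.

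**Conclusion.** The point holds on the plain wording of Section 11.0. The single planned check cannot show whether lost patients differ from retained ones or whether loss depends on diet, and this is true whatever the number lost. Under the assumptions of an equal 1 SD difference in both phases and a two-sided 5% t-test, it flags the difference 5% of the time. A comparison of lost with retained patients flags it 41% of the time at 4 v 18 and 79% at 10 v 40.

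The documents do not show that loss will in fact differ by diet, nor that the main result will be biased. The claim is only that the plan's safeguard could not reveal such a problem. The defect is minor and cheap to correct. It matters more if enrolment follows the 50-patient plan with many dropouts than if it follows the 22-patient plan.

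**What to change.** Replace the sentence in Section 11.0 with wording such as:

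> For each phase, we will compare Visit 1 characteristics of patients not contributing data with those contributing data, and will tabulate the number and timing of losses by diet at loss and by sequence, with the reason where known. The HS-LS comparison will also be shown in patients with data for both phases.

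Two clarifications should go with it:

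- Call the comparison descriptive, since about 4 losses are expected under the 22-patient plan.
- Count every flare withdrawal with an exit visit in the tabulation, even if the patient stays in that phase's analysis by last observation. Wording in terms of contributing data also avoids the definition of dropouts as patients who never return. That definition leaves out the very case the section worries about, a patient present in phase I and absent from phase II.

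The cost is one extra table, one sensitivity analysis and a recorded reason for loss, which no section now plans to collect. Visit 1 characteristics, assigned diet and sequence come from data the trial already gathers. No visit or sample size changes.

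### Section 11's LOCF rule can fill a missing second-diet outcome from the other diet or from washout, Section 11 also excludes such phases, and no passage says which rule governs

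*Combined protocol and SAP*

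**What the plan says.** **Schedule.** Section 6a places visits at weeks 0, 8, 12 and 20. Visits 2 and 4 end the two diet phases. Visit 3 ends the washout, during which patients eat their habitual diet (Section 5f). The sodium MRI is done at visits 2 and 4 only (Section 6, MRI item and Table 1.A).

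**Carry forward.** For patients withdrawn or lost after randomisation, Section 11 says "the last visit after baseline screen will be used to replace missing values (last observation carried forward, LOCF method". It adds that "ANCOVA with LOCF method will be used to analyze the data as a more conservative approach". Section 12 defines the ANCOVA outcome as the end-of-treatment value "or the last observation for patients with early withdrawal as an outcome variable".

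**Exclude.** Section 11 also says, for either or both phases, that "when a patient drops out without having any follow-up data assessed, data points for the patient will be excluded from the analysis". It discusses the consequence: "Possible confounding could occur when a patient is included in the analysis of phase 1 and excluded from phase II due to dropout". It then states that "Dropouts will be defined as patients who are randomized but never return".

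**Other rules.** Section 10 says that an intention-to-treat approach applies to patients lacking week 8 data, without saying what is done with the missing value. It names linear mixed models for the actual analysis.

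**Data after withdrawal.** Section 11: "In the event of withdrawal from the study, no additional collection of information from the date of withdrawal will be performed". Section 5e provides an exit visit for patients withdrawn after a flare, but Table 1.A lists no procedures for it.

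**The concern.** Carrying a value forward makes sense only if an earlier value exists under the same treatment. Here each diet has one scheduled outcome measurement, so a patient without visit 4 has no scheduled second-diet value to carry. The fill is a washout value or the first diet's value. Copying the first diet's skin Na+ scan sets that patient's HS minus LS difference to exactly 0, whatever the diet did.

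Excluding the empty phase, which Section 11 also describes, does not have this effect. Two analysts who both follow the text could therefore report different estimates of the two outcomes that set the sample size, and the choice could be made after the data are seen.

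Calling LOCF more conservative is right for false positives only. The estimate is biased toward no difference and its confidence interval is centred too low.

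**Working it through.** **1. The plan's own figures.** Paired t-test, two-sided 5%, n = 18. Power is the noncentral t tail probability with 17 degrees of freedom and noncentrality difference × √n / SD of differences.
- Skin Na+: 5 × √18 / 5 = 4.24, power 97.9%, against about 98% stated. This takes the quoted SD of 5 as the SD of the paired difference.
- DAS28: no SD is given. Power of 95% for a difference of 1.0 implies an SD of differences of 1.108.
- Allowance: Section 11 says "which we built into our samples size by consenting 22 patients with goal of having at least 18" complete, so at most 4 of 22 are lost. Applying Section 10's 20% to its enrolment of 50 gives 10.

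**2. What can be carried into a missing visit 4.**
- Loss during the second diet: visit 3 for outcomes measured at every visit.
- Loss between visits 2 and 3: visit 2, the other diet.
- Skin Na+: visit 2, whenever the loss occurs, unless an exit visit supplies a scan.
- Weekly home blood pressure is taken on diet, but no section names it as the outcome.

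**3. Paired arithmetic.** A visit 2 fill gives a difference of 0. A visit 3 fill gives half the effect if habitual intake lies midway (an assumption).
- Skin Na+: 5 × 18/22 = 4.09 and 5 × 40/50 = 4.0 mmol/L.
- DAS28, 4 of 22 filled: 18/22 = 0.82, or (18 + 4 × 0.5)/22 = 0.91.
- DAS28, 10 of 50 filled: 40/50 = 0.80, or (40 + 10 × 0.5)/50 = 0.90.
- DAS28, 2 of 22 filled: 20/22 = 0.91, or (20 + 2 × 0.5)/22 = 0.95.

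**4. Section 12 ANCOVA, simulated.** True DAS28 difference 1.0, within-patient SD 1.108/√2 = 0.78, no carryover, loss balanced across sequences, 4,000 runs. Between-patient SD 0.9 and habitual diet midway are assumptions from outside the documents. The model regresses outcome on diet and own-period baseline over both periods.

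| Rule for the missing phase | 4 of 22: estimate | coverage | power | 10 of 50: estimate | coverage |
|---|---|---|---|---|---|
| Visit 2 outcome, visit 1 baseline | 0.81 | 95% | 0.78 | 0.80 | 89% |
| Visit 2 as both | 0.88 | 96% | 0.86 | 0.86 | 92% |
| Visit 3 as both | 0.91 | 95% | 0.88 to 0.89 over repeat runs | 0.90 | 93% |
| Phase excluded | 1.00 | 97% | 0.90 | 1.00 | 97% |

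With 2 of 22 filled, the three fills give about 0.91, 0.94 and 0.96. Varying the between-patient SD from 0.6 to 1.2 moves the 4 of 22 and 10 of 50 estimates by about 0.02 at most. Type I error of the LOCF ANCOVA is about 0.02 to 0.04. A paired analysis at 4 of 22 has 95% power under either fill or exclusion.

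**5. Unbalanced loss.** If all losses fall in one sequence, a visit 3 fill gives 0.82 to 1.00 (4 of 22) or 0.79 to 1.00 (10 of 50), depending on the sequence and the habitual level. So the shrinkage from a visit 3 fill ranges from none to about that of a visit 2 fill.

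**The case against.** The best defence reads Section 11 as covering two populations. Patients who never return are excluded, and patients with some follow-up have their last value carried forward. The definition of dropout and the analysis set of patients with at least one follow-up support this. The reference to either or both phases and the sentence on patients kept in phase 1 but not phase II cut against it. Even if it were accepted, LOCF would still draw on the other diet or on washout.

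A second defence is that LOCF is only a secondary analysis, since it is labelled more conservative and Section 10 names mixed models for the actual analysis. That is possible, but Section 12 places the last observation in the only model it describes, without such a label.

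Two points stand and limit the size.
- For outcomes measured at every visit, loss during the second diet leads to a visit 3 fill. Visit 3 is that period's own baseline, so the fill amounts to zero change, which is milder than copying the other diet.
- The 4 of 22 and 10 of 50 cases are ceilings within the plan's allowance. Section 11 expects loss well under 20%, and patients who never return have no later visit to carry forward.

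**Conclusion.** The point holds as a should-fix. The LOCF rule, as written, can only fill a missing visit 4 with a value from the wrong condition, exit visits aside. The plan also contains an exclusion rule and an unspecified intention-to-treat rule, and does not rank them.

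As an upper bound within the allowance, the DAS28 estimate loses about 9 to 19% (4 of 22 filled) or 10 to 20% (10 of 50, assuming all 50 are randomised and none replaced). Skin Na+ loses 18 or 20%. With 2 of 22 filled, DAS28 loses about 4 to 9%. At 4 of 22, ANCOVA power falls from about 0.90 under exclusion to 0.78 to 0.89, paired power stays near 95%, and coverage is near nominal. At 10 of 50, coverage falls to 89 to 93%.

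A reader might infer more, but the documents do not support it:
- That false positives are inflated. They are not.
- That every fill comes from the other diet. This is so only for skin Na+ and for losses between visits 2 and 3.
- That LOCF is certainly the primary rule. The text leaves this open.
- That enrolling 50 to obtain 18 completers means 32 filled patients, with DAS28 estimates of 0.36 to 0.68. No passage says how many would be lost after visit 2. Section 10 also assumes under 20% loss and replaces any excess.

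**What to change.** Delete the two LOCF sentences in Section 11 and the last-observation alternative in Section 12's ANCOVA sentence. Replace Section 10's intention-to-treat sentence on missing week 8 data with the same single rule: all observed diet phases of randomised patients are analysed as randomised; a phase with no on-diet outcome contributes none; a value from the other diet or from washout is never its outcome.

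Fit the linear mixed model that Section 10 names, with diet, period, own-period baseline where one exists (skin Na+ has none) and a random patient effect. The period term is needed because keeping unpaired first-period data can unbalance diet and period. With all losses in one sequence and an assumed second-period shift of 0.5 to 1.0, checks without the term put the estimate too high by up to about 0.20, depending on how the shift and variances are modelled. With the term it stayed near 1.00. Report the completers' paired analysis as a sensitivity analysis. State whether an exit-visit value counts as the outcome of the diet the patient was on.

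The cost is wording and one degree of freedom; no new data are needed. The downside is reliance on missing at random, which withdrawal for flare may strain. In a worst case where the patients lost are those with the highest unseen visit 4 DAS28, the mixed model without a period term gave 0.92 (4 of 22) and 0.91 (10 of 50). A check of 1,200 runs under the same assumptions, with the period term added, gave about 0.88 in both. LOCF gave 0.77 to 0.87 and 0.76 to 0.86. In that case the proposed model is biased too, and it gains little over a visit 3 fill.
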